7.1.2 Measures to be taken to minimize or avoid bias

Randomization:

The random product attribution will be performed after checking that the eligibility criteria are fulfilled, thus minimizing the selection bias. Each site will receive several treatment blocks in accordance with the randomization table generated by Axiodis (blocks of 4). During the V1 visit, the investigator will deliver a product (active or placebo) to the patient in chronological order using the list of treatments allocated to the respective site. This method allows to maintain the 1:1 balance in a multicentric study.

Example: the site 01 received 3 treatment blocks, i.e. 12 treatments, number 001 to 012. For the patient 01-001, the investigator will deliver the treatment 001. The site 02 received 3 treatments blocks, i.e 12 treatments, number 013 to 025. For the patient 02-001, the investigator will deliver the treatment 013.

Blinding and unblinding:

The randomization list will be drawn up using a validated software and before the beginning of the study, by a statistician (at Axiodis) not involved in the study. The master randomization list will be stored confidentially until the study blind is broken at the end of study.

The randomization list will be:

- Transmitted by the Axiodis statistician to the person in charge of the product preparation,
 Creapharm
- Uploaded into the patient unblinding module of the eCRF

During the whole study and in the absence of unblinding, neither the investigators nor the subjects nor the staff involved (CRO, sponsor...) will be aware whether the product is Healsea® Babykids or the Placebo. Every effort will be made to maintain the blind during the study as well as during the follow-up period.

Both Medical Devices (Healsea® Babykids and Placebo) will be indistinguishable: same aspect, same packaging and same labelling of the vials.

The unblinding will occur after the database locking, at the end of the study. The statistician responsible for the randomization list will be in charge of the unblinding.

Emergency Unblinding:

In case of a medical emergency where knowledge of the blinded treatment is necessary for the treatment of an adverse event/incident, the investigator shall perform the unblinding via the unblinding module of the eCRF. The investigator shall send an e-mail informing about the unblinding with patient ID, date and reason of unblinding (the name of patient not to be communicated for GDPR compliance) to:

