6.3. Statistical/Analytical issues

6.3.1. Significance level

All statistical analyses will be performed at the 0.05 global significance level (type I error rate), using two-sided tests.

The statistical results will only allow to conclude on the primary efficacy criterion. All other statistical results have to be considered within a descriptive perspective and not as inferential issues. No adjustment for Type I error will be done. P-values of statistical tests on secondary criteria will be provided for information only.

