6.3.4. Multicentre studies and Adjustment for covariates

No adjustment on centre will be performed.

AXIODIS CRO 10/47

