8.4. Acute Rhinitis Symptoms Severity Questionnaire

The scores to each of the ten items of the ARSSQ, the score of cold symptoms (the sum of the scores to the items 2 to 7), the score of impact on Quality-of-Life (the sum of the scores to the items 8 to 10) and the global score (the sum of the scores to all the ten items) will be described at baseline.

A Student (or Wilcoxon if the normality assumption is not acceptable) between-groups test will be performed for each score.

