10. EFFICACY

10.1. Analysis of the primary efficacy criterion

The primary objective will be analysed by performing a t-test (or a Wilcoxon test if the normality assumption is not acceptable) on the means of AUC on global score of ARSSQ during the first eleven days of the study between treatment groups.

The answers of the ten items of ARSSQ are scored from 0 to 3 (0: negative answer; from 1 to 3: positive answer with an increasing severity level). See the daily report in appendix (§13.3). The global ARSSQ score at each time point is the sum of the scores to the ten items of the ARSSQ:

At each time point t: ARSSQTOT(t) =
$$\sum_{j \text{ in } \{1; ...; 10\}} ARSSQ_j(t)$$

AUC of global ARSSQ score will be computed by the method described in §6.4.7.

Patients will be analysed on the FAS and the PP Set. In each case, boxplots of the AUC on global score will be realized by treatment group. The number of available data and the p-value will be printed on the figure.

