10.2. Analysis of the secondary efficacy criteria

The analysis of the secondary efficacy criteria will involve multivariate analysis.

The selection of variables in multivariate analysis will be performed using a 0.20 significance level and a stepwise method. Covariates considered as potential confounding factors to be initially tested with the treatment in the multivariate models are:

- Body temperature at baseline (°C);
- Scores to each of the items 2 to 7 of the ARSSO at baseline.

All multivariate analyses below will follow this logic.

10.2.1. Modelling of AUC on global score by multivariate ANCOVA

A multivariate ANCOVA model of the AUC on global score of ARSSQ during the first eleven days of the study will be performed.

Patients will be analysed on the FAS and the PP Set.

AXIODIS CRO 17/47

10.2.2. Durations of cold symptoms and of impacts on Quality-of-Life

Hereinafter, the "recovery date" is the first day of the two first consecutive days the patient gave a negative answer to the question 1 ("not sick") without giving a positive answer to the same question (other than "not sick") later. Otherwise, there is no "recovery date" for the patient.

The scores of cold symptoms and of impact on Quality-of-Life (QoL) will be computed at each time-point the patient completed the questionnaire (see §6.4.6), using the following formulae:

At each time point t: ARSSQ_{SYMP}(t) =
$$\sum_{j \text{ in } \{2; ...; 7\}} ARSSQ_{j}(t)$$

ARSSQ_{QOL}(t) = $\sum_{j \text{ in } \{8; ...; 10\}} ARSSQ_{j}(t)$

• The duration of common cold is defined as the duration between the reference start date and the recovery date.

Common cold's duration (days) = Recovery date - Reference start date

The origin date will be the reference start date.

The considered event is the end of common cold, i.e. the recovery of the patient. The event date will be the last day before the recovery date.

Patients without recovery date will be censored at D18 or at the end of the study, and the censoring date will be the date of D18 or the reference end date, whichever occurs first.

• The duration of the cold symptoms is defined as the duration between first symptomatic day and last symptomatic day.

Cold symptom's duration (days) = Last symptomatic day - first symptomatic day + 1

The first symptomatic day is the first day the patient had a non-zero and non-missing score of cold symptoms. It will be the origin date.

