12. CHANGES IN THE CONDUCT OF THE STUDY OR PLANNED ANALYSIS

The planned analysis in the protocol to assess the primary objective (multivariate ANCOVA model of the AUC on global score of ARSSQ during the first eleven days of the study) has been replaced by the comparison of the means of the AUC on global score of ARSSQ during the first eleven days of the study between treatment groups. The multivariate ANCOVA has been put among secondary analyses.

This change has no impact on the relevance of the sample size calculation since the primary endpoint is the same as planned in the protocol.

Moreover, since several patients still reported having symptoms while they reported they did not feel sick anymore at the question 1 during at least the two last days of completion of the ARSSQ, their positive answers to the cold symptoms' items have been considered as non-significant. Consequently, the question 1 has been taken into account in addition to the corresponding items to determine the end of the cold symptoms' duration, however only on the condition that the last days of completion were consecutive.

If the last days of completion were not consecutive, positive answers to cold symptoms' items are still considered as symptomatic, even if the two last answers to the question 1 are negative. The symptom ends at the last symptomatic day if the patient reported the absence of this symptom at least twice and consecutively after this day. Otherwise, the duration of the symptom is censored at D18 or at the end of the study, whichever occurs first.

The same change has been applied to compute the duration of impact on QoL.

AXIODIS CRO 25/47

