At D12 evening	XX (XX.X%)	XX (XX.X%)	XX (XX.X%)
After D12	XX (XX.X%)	XX (XX.X%)	XX (XX.X%)

AXIODIS CRO 40/47

Mock T13

	Healsea Babykids N=XX	Placebo N=XX	Total N=XX
AUC on global score of ARSSQ			
N	XX	XX	XX
Missing	XX	XX	XX
Mean (SD)	XX.X (XX.X)	XX.X(XX.X)	XX.X (XX.X)
Median	XX	XX	XX
Q1/Q3	XX / XX	XX / XX	XX / XX
Min/Max	XX / XX	XX / XX	XX / XX
Between-groups test	XXX (Student/Wilcoxon)		

Mock F2

AXIODIS CRO 41/47

Mock T14

[figure not shown]
	Healsea Babykids N=XX	Placebo N=XX
AUC on global score of ARSSQ		
ANCOVA model :		
AUC = Treatment +		
Type 3 Tests of Fixed Effects		
Treatment	XXX	
	XXX	
Adjusted mean		
LSMeans (SE)	XX.X (XX.X)	XX.X (XX.X)
[LSM 95%CI]	[XX.X; XX.X]	[XX.X; XX.X]
Adjusted mean (diff. vs Placebo)		
LSMeans (SE)	XX.X (XX.X)	
[LSM 95%CI]	[XX.X; XX.X]	
Contrast vs Placebo, p=	XXX	

Mock T15

	Healsea Babykids N=XX	Placebo N=XX
Duration of common cold / cold symptoms / impact of	on Quality-of-Life	
N	XX	XX
Missing	XX	XX
Mean (SD)	XX.X (XX.X)	XX.X (XX.X)
Median	XX	XX
Q1/Q3	XX / XX	XX / XX
Min/Max	XX / XX	XX / XX
Cox survival regression model:		
Hazard Ratios [95%CI]		
Treatment	XX.X [XX.X; XX.X]	
	XX.X [XX.X; XX.X]	
p-values (Wald)		
Treatment	XXX	
	XXX	

AXIODIS CRO 42/47

[figure not shown]
Mock F3

For Treatment: the reference is Placebo

AXIODIS CRO 43/47

Mock F4

AXIODIS CRO 44/47

Mock T16

	Healsea Babykids N=XX	Placebo
Use of XXX	N=XX	N=XX
N	XX	XX
Missing	XX	XX
No	XX.X (XX.X%)	XX.X (XX.X%)
Yes	XX.X (XX.X%)	XX.X (XX.X%)
Logistic model :		,
Odds Ratios [95%CI]		
Treatment	XX.X [XX.X; XX.X]	
	XX.X [XX.X; XX.X]	
p-values (Wald)		
Treatment	XXX	
	XXX	
Number of days of intakes of XXX		
N	XX	XX
Missing	XX	XX
0	XX.X (XX.X%)	XX.X (XX.X%)
1	XX.X (XX.X%)	XX.X (XX.X%)
2	XX.X (XX.X%)	XX.X (XX.X%)
	XX.X (XX.X%)	XX.X (XX.X%)
Poisson regression :		
Type 3 Tests of Fixed Effects		
Treatment	XXX	
	XXX	

AXIODIS CRO 45/47

Mock T17

	Healsea Babykids N=XX		ls Placebo N=XX		Total N=XX	
	n (%)	[E]	n (%)	[E]	n (%)	[E]
Number and percentage of patients with / Number of (non-related)						
Incident (Adverse event)	XX (XX.X%)	XXX	XX (XX.X%)	XXX	XX (XX.X%)	XXX
Incident (Adverse event) leading to definitive study device discontinuation	XX (XX.X%)	XXX	XX (XX.X%)	XXX	XX (XX.X%)	XXX
Incident (Adverse event) leading to definitive study discontinuation	XX (XX.X%)	XXX	XX (XX.X%)	XXX	XX (XX.X%)	XXX
Serious incident (adverse event)	XX (XX.X%)	XXX	XX (XX.X%)	XXX	XX (XX.X%)	XXX
(Treatment-emergent adverse event)	XX (XX.X%)	XXX	XX (XX.X%)	XXX	XX (XX.X%)	XXX

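### The primary AUC test leaves out the D1 global ARSSQ score and the site used for blocking, and its table shell reports no between-group difference or confidence interval

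*SAP*

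**What the plan says.** SAP 10.1 compares the arms by "performing a t-test (or a Wilcoxon test if the normality assumption is not acceptable) on the means of AUC on global score of ARSSQ", with no covariates. SAP 6.3.1 makes this the sole basis for inference: "The statistical results will only allow to conclude on the primary efficacy criterion". SAP 6.3.4 adds "No adjustment on centre will be performed".

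Allocation is nevertheless organised by site. Protocol 7.1.2 says "Each site will receive several treatment blocks in accordance with the randomization table generated by Axiodis (blocks of 4"), and Protocol 7.1.7 gives 8 sites. The baseline score is also available. Under SAP 8.4, "the global score (the sum of the scores to all the ten items) will be described at baseline".

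Mock T13, the primary table shell, lists N, missing, mean (SD), median, quartiles and range per arm, plus one entry for the test. The boxplot adds only the number of observations and the p-value. The row "Adjusted mean (diff. vs Placebo"), with its 95% CI, appears only in Mock T14, the shell for the secondary ANCOVA. SAP 10.2 builds that model by selection: "The selection of variables in multivariate analysis will be performed using a 0.20 significance level and a stepwise method". Its candidates are body temperature and baseline items 2 to 7.

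Protocol 8.3 had planned a regression model of the AUC as the primary analysis, without naming covariates. SAP 12 records the replacement and states "The multivariate ANCOVA has been put among secondary analyses". It says the sample size is unaffected because the endpoint is unchanged, but gives no reason for the change.

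**The concern.** Four things follow from these passages.

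- **Baseline.** The D1 global score is a pre-treatment measure of the same quantity as the outcome. Leaving it out forgoes whatever precision it would bring. It cannot enter the secondary ANCOVA either, because only six of the ten items are candidates and only as separate items.
- **Site.** Blocking within site balances the arms within each site. An analysis that ignores site leaves between-site variance in the standard error, so the test is conservative if sites differ.
- **Reporting.** The one result that supports a conclusion would appear without an effect size or confidence interval. The only difference with a CI comes from a descriptive model whose covariates are not known in advance.
- **Wilcoxon switch.** The Wilcoxon test does not compare means, no criterion for unacceptable normality is given, and no matching effect estimate is named.

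The sample size has no dropout allowance and withdrawn children are not replaced (Protocol 7.3.1.5), so the plan has little power to spare.

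**Working it through.** **Inputs from the documents.** d = 0.4, two-sided 5%, 80% power, 100 per arm (SAP 4, SAP 6.3.1); 8 sites (Protocol 7.1.7). The AUC is standardised to SD 1, because no SD in score units is given.

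**Assumed inputs.** r is the correlation of the D1 global score with the AUC. ICC is the share of AUC variance due to site. The documents give neither, so ranges are shown.

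**1. The plan's own figure.** Noncentrality = d × √(n/2) = 0.4 × √50 = 2.828 on 198 df, so power is 80.4%. The stated sample size reproduces, and it is a calculation for an unadjusted comparison. With fewer children analysed:

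| Analysed per arm | 100 | 99 | 95 | 90 |
|---|---|---|---|---|
| Power | 80.4% | 79.97% | 78.3% | 76.1% |

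**2. Adding baseline and site, with no site differences.** The residual SD becomes √(1 − r²). The model has 10 parameters (intercept, treatment, baseline, 7 site terms), so df = 200 − 10 = 190. Noncentrality = 2.828 / √(1 − r²). The CI width ratio is √(1 − r²).

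| r | Noncentrality | Power, 100 per arm | CI width ratio |
|---|---|---|---|
| 0.1 | 2.843 | 80.7% | 0.995 |
| 0.2 | 2.887 | 81.9% | 0.980 |
| 0.3 | 2.965 | 83.9% | 0.954 |
| 0.4 | 3.086 | 86.7% | 0.917 |
| 0.5 | 3.266 | 90.1% | 0.866 |

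At r = 0.3, power is 82.0% with 95 per arm and 79.9% with 90.

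**3. What r might be.** The AUC is a trapezoid over D1 to D11 (SAP 6.4.7), so D1 enters with weight ½. With equal daily variances and independent days, r = 0.5 / √(0.25 + 9 + 0.25) = 0.16. With first-order day-to-day autocorrelation of 0.5 or 0.7, r is about 0.30 or 0.43. This is an illustration, not an estimate.

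**4. Site.** With balance within site, the large-sample type I error of the unadjusted test is 2 × [1 − Φ(1.96 / √(1 − ICC))]. Site-adjusted power uses noncentrality 2.828 / √(1 − ICC) on 191 df. The simulation used 8 sites of 25 children, blocks of 4 within site and 20,000 runs per cell. Its Monte Carlo SE is about 0.15 points for type I error and 0.3 for power.

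| ICC | Type I, unadjusted: formula / simulated | Type I, site-adjusted: simulated | Power, unadjusted: simulated | Power, site-adjusted: formula / simulated |
|---|---|---|---|---|
| 0.05 | 4.4% / 4.6% | 5.2% | 81.0% | 82.3% / 82.1% |
| 0.10 | 3.9% / 4.3% | 5.2% | 81.5% | 84.3% / 84.0% |
| 0.15 | 3.4% / 3.7% | 5.2% | 82.8% | 86.3% / 86.6% |

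Comparing simulated with simulated, site adjustment gains 1.1, 2.4 and 3.8 points.

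**5. Both together,** r = 0.3 within site and ICC = 0.10: noncentrality 2.828 / √(0.91 × 0.90) = 3.125 on 190 df, so power is 87.5%. Simulation gives 87.2%, against 81.9% for the t-test.

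**6. The interval T13 does not show.** The half-width for the unadjusted difference is 1.972 × √(2/100) = 0.28 SD, which matters in a trial planned around 0.4 SD.

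**7. Is the covariate usable?** SAP 6.4.7 sets the AUC to missing without a D1 value, so every child with an AUC has the covariate. Protocol 7.1.3 places the D1 questionnaire at visit V1, and Protocol 7.4.1 places first device use that evening, so it is pre-treatment.

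**The case against.** The strongest reply is that nothing here is an error. The sample size is built on the standardised difference in AUC between arms, which is what an unadjusted t-test examines, and that test needs no choice of covariates. The benefit depends on r and ICC, which the documents do not supply. Entry criteria narrow the D1 range, which may lower r, and at r = 0.1 the gain is 0.3 points. Unadjusted power with site variance stays above plan, and a conservative test does not endanger a positive claim. Few children should lack an AUC, since SAP 6.4.7 needs only D1 and one later value. A baseline-adjusted ANCOVA with a difference and CI is already planned in T14. The unadjusted difference and CI can be derived from the N, mean and SD in T13.

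Much of this stands. The test is valid, the covariate gain may be small, and losses from the primary analysis are likely to be limited. What it does not answer is the following. T14 comes from a stepwise model that the SAP treats as descriptive and that cannot include the global score or site. An interval that readers must derive themselves is not a reported result, and T13 offers nothing equivalent if the Wilcoxon test is used. SAP 12's remark on sample size does not explain why the protocol's regression was dropped.

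**Conclusion.** The concern holds, as forgone precision and incomplete reporting rather than invalidity. The unadjusted test meets the planned power only if nearly all 100 per arm are analysed; at 99 it is just under 80%. Against 80.4%, adjustment for baseline and site would give 80.7% to 90.1% power over assumed r of 0.1 to 0.5 without site differences. Site differences at an assumed ICC of 0.05 to 0.15 would bring the unadjusted type I error down to about 4.4% to 3.4%. These sizes rest on the assumed r and ICC, and the simulations also on equal site enrolment. The missing difference and CI for the confirmatory result, and the missing reason for the change, rest on no assumption. The change should be made; confidence in the size of the gain is medium.

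**What to change.** - In SAP 10.1, make the primary analysis a fixed ANCOVA: AUC = treatment + D1 global ARSSQ score + site, with no stepwise selection and no switch driven by a normality check.
- Define the D1 covariate as the questionnaire completed at V1, before first device use that evening. The definition is needed because the protocol synopsis and Protocol 7.4.1 also describe evening diary completion from D1.
- In Mock T13, report the adjusted mean difference versus Placebo with its 95% CI and p-value.
- Delete the sentence in SAP 6.3.4 that excludes centre adjustment.
- Keep the unadjusted t-test as a sensitivity analysis.
- In SAP 12, state why the primary analysis differs from the protocol, and date this before unblinding.

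The cost is SAP wording, one table shell and 8 of 198 residual degrees of freedom (198 − 190). No new data are needed, and no child with a computable AUC is lost.

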10.2. Analysis of the secondary efficacy criteria

The analysis of the secondary efficacy criteria will involve multivariate analysis.

The selection of variables in multivariate analysis will be performed using a 0.20 significance level and a stepwise method. Covariates considered as potential confounding factors to be initially tested with the treatment in the multivariate models are:

- Body temperature at baseline (°C);
- Scores to each of the items 2 to 7 of the ARSSO at baseline.

All multivariate analyses below will follow this logic.

10.2.1. Modelling of AUC on global score by multivariate ANCOVA

A multivariate ANCOVA model of the AUC on global score of ARSSQ during the first eleven days of the study will be performed.

Patients will be analysed on the FAS and the PP Set.

AXIODIS CRO 17/47

10.2.2. Durations of cold symptoms and of impacts on Quality-of-Life

Hereinafter, the "recovery date" is the first day of the two first consecutive days the patient gave a negative answer to the question 1 ("not sick") without giving a positive answer to the same question (other than "not sick") later. Otherwise, there is no "recovery date" for the patient.

The scores of cold symptoms and of impact on Quality-of-Life (QoL) will be computed at each time-point the patient completed the questionnaire (see §6.4.6), using the following formulae:

At each time point t: ARSSQ_{SYMP}(t) =
$$\sum_{j \text{ in } \{2; ...; 7\}} ARSSQ_{j}(t)$$

ARSSQ_{QOL}(t) = $\sum_{j \text{ in } \{8; ...; 10\}} ARSSQ_{j}(t)$

• The duration of common cold is defined as the duration between the reference start date and the recovery date.

Common cold's duration (days) = Recovery date - Reference start date

The origin date will be the reference start date.

The considered event is the end of common cold, i.e. the recovery of the patient. The event date will be the last day before the recovery date.

Patients without recovery date will be censored at D18 or at the end of the study, and the censoring date will be the date of D18 or the reference end date, whichever occurs first.

• The duration of the cold symptoms is defined as the duration between first symptomatic day and last symptomatic day.

Cold symptom's duration (days) = Last symptomatic day - first symptomatic day + 1

The first symptomatic day is the first day the patient had a non-zero and non-missing score of cold symptoms. It will be the origin date.

The last symptomatic day is defined as the day before the two first consecutive days the patient had a zero score of cold symptoms without having a non-zero and non-missing score of cold symptoms later. The considered event is the end of cold

AXIODIS CRO 18/47

symptoms, i.e. the definitive nullification of the corresponding score during at least two consecutive days.

The considered symptomatic days are between D1 and either D18, or the end of the study, or the day before the recovery date, whichever occurs first. Symptomatic days from the recovery date will not be taken into account.

For patients who definitely nullified the score of cold symptoms, or for patients with a recovery date, the event date will be the last day before the definitive nullification of the score of cold symptoms, or before the recovery date if it exists.

Patients who did not definitely nullify the score of cold symptoms, and without recovery date, will be censored at D18 or at the end of the study, and the censoring date will be the date of D18 or the reference end date, whichever occurs first.

For patients who never had a non-zero score of cold symptoms (never ticked "mild", "moderate" or "severe" for any symptom) and having completed the questionnaire at D1, the origin date for the symptom will be D1, the cold symptoms will be censored at D1 and the duration will be zero. If patients who never reported the presence of any symptom did not complete the questionnaire at D1, neither origin date nor censoring date will be defined for cold symptoms and the duration will be missing.

• The duration of impact on QoL is defined as the duration between first impacted day and last impacted day.

Impact on QoL's duration (days) = Last impacted day – first impacted day + 1

The first impacted day is the first day the patient had a non-zero and non-missing score of impact on QoL. It will be the origin date.

The considered event is the end of impact on QoL, i.e. the definitive nullification of the corresponding score during at least two consecutive days. The last impacted day is defined as the day before this definitive nullification, and the duration is computed by the same way as for cold symptoms' duration.

A Cox survival regression model will be used to analyse each of the durations of common cold, of cold symptoms and of impact on QoL.

Since the computed duration in the three cases is a recovery time and not a survival time, unlike the usual case of application of Cox survival regression, the provided hazard ratios will measure the likeliness of the recovery.

Consequently, and particularly for the treatment (with Placebo as reference), a hazard ratio greater than 1 will have to be considered under a positive aspect, because it will significate that the recovery is more likely under Healsea[®] Babykids treatment than under Placebo. On the contrary, a hazard ratio lower than 1 will have to be considered under a negative aspect.

For the three durations, a forest plot of the hazard ratios and their 95% CIs from the final multivariate Cox survival regression model will be provided.

AXIODIS CRO 19/47

In addition, for the three durations, a Kaplan-Meier graph will be provided. Survival curves will be drawn by treatment group. Number of sick / symptomatic / impacted patients, number of events (recoveries) and number of censors in each arm will be displayed on the same graph, as well as the log-rank p-value.

For the same reason as above and unlike the usual case of application of Kaplan-Meier graph, if the log-rank p-value is under 5%, a survival curve for Healsea[®] Babykids group under the curve for Placebo group will have to be considered under a positive aspect, and the contrary under a negative aspect.

Patients will be analysed on the FAS.

AXIODIS CRO 20/47

Statistical Analysis Plan

10.2.3. Use and number of days of use of conventional common cold medications

A multivariate logistic regression model will be used to analyse use (yes/no) of conventional common cold medications (overall and by therapeutic class: antibiotics, antipyretics, mucolytics, decongestants, antitussives, systemic and topical corticosteroids).

BASICC

A multivariate Poisson regression model will be used to analyse the number of days of use of conventional common cold medications (overall and by therapeutic class).

The number of days of use of these medications is defined as follows:

- A day is counted when the patient used at least one of these medications this day;
- Each day is counted once, whatever the number of these medications used this day;
- The total number is the sum of all distinct days of use of these medications, from D1 to D18.

Patients will be analysed on the FAS.

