6.4.7. AUC on global score of ARSSQ

The computation of the AUC on global score of the questionnaire will be made for patients with non-missing value at D1 and at least another non-missing time point between D2 and D11. Otherwise, the AUC will be missing.

The AUC will be computed by the trapezoidal rule from D1 to D11 (Acute Phase).

If the value at D11 is missing, then it will be estimated by the value at the last non-missing time point before D11.

AXIODIS CRO 13/47

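### Covariates in the secondary models are chosen stepwise at 0.20, model by model, from a list that omits the outcome's own baseline for two Cox models and part of it for the AUC

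*SAP*

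**What the plan says.** SAP 10.2 sets one rule for the secondary efficacy models: "The selection of variables in multivariate analysis will be performed using a 0.20 significance level and a stepwise method". It offers seven candidates: baseline body temperature and "Scores to each of the items 2 to 7 of the ARSSO at baseline". On scope it says: "All multivariate analyses below will follow this logic". The section and the table list in SAP 13.1 show what follows the rule:

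- ANCOVA of the AUC, on the FAS and on the PP Set (2 fits)
- Cox models for duration of common cold, of cold symptoms and of quality-of-life impact (3)
- logistic models for medication use, overall and for six classes (7)
- Poisson models for days of medication use, on the same split (7)

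The total is 2 + 3 + 7 + 7 = 19.

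The outcomes are built from more of the questionnaire than the candidates are. SAP 10.1: "The global ARSSQ score at each time point is the sum of the scores to the ten items of the ARSSQ". SAP 10.2.2 defines the end of the common cold by question 1, the end of cold symptoms mainly by the sum of items 2 to 7, and the end of quality-of-life impact mainly by the sum of items 8 to 10. The unused baseline scores are available: SAP 8.4 has every item, both sub-scores and "the global score (the sum of the scores to all the ten items) will be described at baseline".

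The protocol (8.3 and 8.4) names the model types but gives no covariates and no selection rule.

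**The concern.** Two things are wrong with the rule.

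**The models are not prespecified.** The outcome data choose the covariates afresh in each fit. The FAS and PP versions of the same ANCOVA, which exist to be compared, can end up adjusting for different variables. So can the models for different medication classes. A 0.20 threshold also lets noise variables in easily.

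**The list does not match the endpoints.** SAP 10.2 presents the candidates as possible confounders. In a randomised trial covariates mainly serve precision, and the natural first candidate is the baseline value of the outcome. For two Cox models that value cannot enter at all, and for the AUC only part of it can. At stake are the precision of those adjusted estimates, the size of the hazard ratios (which depends on what is adjusted for) and a stable definition of what each estimate measures.

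**Working it through.** **1. Which outcomes have their own baseline on the list**

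| Endpoint | Built from | Own baseline offered |
|---|---|---|
| AUC of global score | items 1-10 | 6 of 10 components |
| Duration of common cold | question 1 | none |
| Duration of cold symptoms | items 2-7 | all, item by item |
| Duration of quality-of-life impact | items 8-10 | none |
| Medication use and days | diary medication records | no ARSSQ score is its own baseline |

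For the AUC the baseline is also part of the outcome, because the trapezoidal rule starts at D1 (SAP 6.4.7). With daily points D1 has weight 0.5 out of 10, or 5%.

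**2. The plan's own figure.** SAP 4 gives 100 per arm, d = 0.4, 80% power and 5% type I error; SAP 6.3.1 makes tests two-sided.

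- n per arm = 2(1.960 + 0.842)² / 0.4² = 98.1, so 99. The exact t-test needs 99.08, so 100.
- Power at 100 = Φ(0.4√50 − 1.960) = Φ(0.868) = 80.7% (80.4% by the t-test).

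The figure reproduces, and this point does not touch it.

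**3. Benchmark for full adjustment.** If the baseline global score correlates ρ with the AUC, the standard error falls by the factor √(1 − ρ²) and power = Φ(0.4√50/√(1 − ρ²) − 1.960). This gives 84.3% at ρ = 0.3, 90.4% at 0.5 and 97.7% at 0.7. The documents do not give ρ.

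**4. AUC: the SAP list against the forced global score.** Simulated with 200 children and ten 0-3 items driven by a common severity, blocked nose at least moderate (the inclusion criterion), d = 0.4, treatment kept in, 400 runs per cell. Inter-item correlation is also assumed. The AUC is generated from the baseline global score, which favours that covariate. Mean standard errors:

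| Inter-item corr. | ρ | None | SAP list | Global forced | SAP ÷ global |
|---|---|---|---|---|---|
| 0.1 | 0.3 | 0.1412 | 0.1371 | 0.1349 | +1.6% |
| 0.1 | 0.5 | 0.1419 | 0.1297 | 0.1227 | +5.7% |
| 0.1 | 0.7 | 0.1414 | 0.1155 | 0.1012 | +14% |
| 0.3 | 0.3 | 0.1412 | 0.1358 | 0.1348 | +0.7% |
| 0.3 | 0.5 | 0.1413 | 0.1265 | 0.1229 | +2.9% |
| 0.3 | 0.7 | 0.1417 | 0.1089 | 0.1009 | +8% |
| 0.5 | 0.3 | 0.1416 | 0.1355 | 0.1352 | +0.2% |
| 0.5 | 0.5 | 0.1408 | 0.1242 | 0.1222 | +1.6% |
| 0.5 | 0.7 | 0.1419 | 0.1060 | 0.1012 | +5% |

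At ρ = 0.5 simulated power was 86-89% with the SAP list, 89-91% with the global score forced in and 78-82% with no covariates. With no treatment effect (ρ = 0.5, 1,500 runs) rejection was 5.4-6.5%, 4.1-5.2% and 4.9-5.8% respectively. The Monte Carlo error there is √(0.05 × 0.95/1500) ≈ 0.6 points.

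**5. Quality-of-life duration (Cox).** Two independent simulations used n = 200 and a conditional hazard ratio of 1.4. The effect of the baseline quality-of-life score on the log hazard, per SD, is assumed.

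- 400 trials per scenario, inter-item correlation 0.1-0.5. At 0.4 per SD: SAP list 58-62% power (HR 1.38-1.39), own baseline 65-66% (HR 1.40-1.42). At 0.7 per SD: 44-49% (HR 1.31-1.33) against 60-67% (HR 1.39-1.42).
- 500 trials per scenario, inter-item correlation 0.1-0.6, Weibull times. At 0.4 per SD: 55-60% against 62-63%, a gap of 3-8 points. At 0.7 per SD: a gap of 9-21 points.

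The Monte Carlo error of a single power figure is √(0.6 × 0.4/400) ≈ 2.4 points, or 2.2 points with 500 trials.

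**6. How unpredictable the selected model is.** Seven candidates give 2⁷ = 128 possible sets. In the 400-trial simulation stepwise selection chose 90-104 different sets per scenario, and the commonest appeared in at most 11% of trials.

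**The case against.** The strongest reply is that little depends on these models. SAP 6.3.1 confines inference to the primary criterion and treats all other results as descriptive. The primary test in SAP 10.1 has no covariates. Selection-free results accompany the AUC (t-test or Wilcoxon) and the three durations (Kaplan-Meier and log-rank). The SAP list also recovers most of the available gain for the AUC: the sum of items 2 to 7 correlated 0.84-0.96 with the global score in simulation, and the list beat no adjustment in every cell.

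All of that stands, and it limits the severity. It does not remove the point. SAP 10.2.2 tells readers how to judge a hazard ratio above or below 1 and plots the final-model ratios with 95% intervals. The ANCOVA was the protocol's planned primary analysis (SAP 12) and is now the only adjusted analysis of that endpoint. A descriptive estimate still needs a fixed definition.

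A reader might infer four stronger things, which the documents do not support:

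- *That no secondary model is offered its outcome's baseline.* Cold-symptom duration has all six items, the AUC has six of ten, and for medication use the only objection is the selection.
- *That precision losses are as large as √(1 − ρ²) suggests* (5%, 13% and 20% at correlations of 0.3, 0.5 and 0.6). That formula compares with no adjustment, whereas the SAP already adjusts.
- *That treatment could be selected out.* SAP 10.2 has covariates tested alongside treatment, and mock tables T14 to T16 carry a treatment row. The text should still say so.
- *That the smaller hazard ratios are biased.* They reflect a different conditioning set (non-collapsibility).

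**Conclusion.** The point holds in limited form and is minor. The 19 adjusted fits are not fixed in advance. Two Cox models cannot use their outcome's own baseline, and the AUC ANCOVA can use only part of it.

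The size is conditional on correlations and baseline effects that the documents do not state:

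- **AUC:** standard error about 0-6% above forced global-score adjustment for assumed ρ up to 0.5, and 5-14% at 0.7.
- **Quality-of-life duration:** about 3-8 points of power at a log-hazard effect of 0.4 per SD, and about 9-21 points at 0.7.
- **Duration of common cold:** not simulated. The reasoning is the same, but question 1 is a single four-level item and its predictive value is unknown.
- **Type I error:** near 5%, with at most slight inflation from selection.

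One limit applies to the quality-of-life result. SAP 10.2.2 starts that duration on the first impacted day, which may fall after D1. For those children a complete D1 score would be zero and would precede the episode, so it would predict less than in the simulation.

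**What to change.** In SAP 10.2, replace stepwise selection with a prespecified covariate set and state that treatment is always retained:

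- AUC: body temperature and baseline global score, identical on FAS and PP
- Duration of common cold: body temperature and baseline question 1
- Duration of cold symptoms: body temperature and baseline sum of items 2 to 7
- Duration of quality-of-life impact: body temperature and the D1 sum of items 8 to 10, with a note that the time origin may be later than D1
- Medication use and days of use: one fixed set, the same overall and for every class

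The cost is SAP wording only. Every variable is collected at Visit 1 and already described under SAP 8.4 and 8.5, and neither the sample size nor the primary test changes.
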